3.3 Dosing algorithm

The goal of the lead-in phase Ib is to determine the MTD and RP2D. We will first treat 6 patients at dose level 0 in the phase Ib. If DLT occurs in $\geq 2/6$ patients, this dose level would exceed the MTD, and 6 patients will be treated at the next lower dose level (i.e. dose level -1). If DLT occurs in $< 2/6$ patients at dose level 0, the next cohort of 6 patients will be treated at the next higher dose level (i.e. dose level +1). The dose escalation or de-escalation (Table 1) will continue in cohorts of 6 until we reach the highest dose level at which $< 2/6$ patients experience a DLT in the first 28 days. The highest dose level at which 0-1/6 patients experience a DLT in the first 28 days of treatment will be the MTD. The RP2D will be selected from among the doses evaluated after reviewing the efficacy, safety, pharmacodynamics data. The RP2D selected may be lower than the MTD. The RP2D will be used to treat an additional 20 patients in the phase II expansion portion of the study.

If $\geq 2/6$ patients experience DLT at dose level -1, the study may be revised to consider additional lower dose levels.

Patients that are removed from study before day 28 for any reason other than toxicity and have not experienced DLT will be replaced.

*With up to 1 potential dose escalation level (+1) to be studied and up to 6 patients to be treated at a given dose, the target maximum number of patients projected to be enrolled in the phase Ib part of the trial will be 12.

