5.1 Schedule

All patients will be registered through CORe.

The Phase Ib dose escalation stage of the study will evaluate the safety, tolerability, PD and PK of venetoclax in combination with quizartinib, with the objectives of identifying the MTD and RP2D for each combination.

Quizartinib will be administered orally daily continuously starting on cycle 1 day 1. Patients will self-administer quizartinib tablets orally QD. If a dose is missed or vomited, the next dose should not be increased to account for missing a dose. The subject should take the next regular dose at the regularly scheduled time. Patients will receive one cycle of therapy every 28 days (+/- 7 days). Cycle 1 Day 1 of each cycle will be counted from the start of the quizartinib dosing. Quizartinib dose escalation criteria will be maintained as suggested in quizartinib Investigational Brochure (IB) as follows:

1. If the target dose for the given patient in the phase IB or phase II portion is quizartinib 30mg the patient will start the dosing on C1D1 at quizartinib 30mg per day
2. If the target dose for the given patient in the phase IB or phase II portion is quizartinib 60mg the patient will start the dosing on C1D1 at quizartinib 30mg per day and can increase to quizartinib 60mg per day on C1D12 only if QTcF on triplicate ECG is <450 msec on the Day 12 post-dose EKG

The initiation of venetoclax will be deferred for 7 days in cycle 1 to allow clinical and correlative evaluation of quizartinib single agent activity, and to debulk tumor burden thereby reducing the risk of tumor lysis syndrome (TLS). The intent is to initiate venetoclax on cycle 1 day 8. Blood samples will be collected at pre-dose, 2 (+/- 30 minutes), 4 (+/- 30 minutes), 6(+/- 30 minutes), 8 (+/- 30 minutes) and 24 (+/- 30 minutes) hours post-dose on cycle 1 day 14 to measure venetoclax, quizartinib and AC886 concentrations in patients enrolled in the dose-escalation period (n=12). The WBC count must be <10K prior to the initiation of venetoclax dosing. Note: Hydroxyurea can be used if needed during these initial 7 days to control WBC count, if needed.

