5.5.4 Tumor Lysis Prophylaxis

There is a potential for TLS in patients treated with venetoclax, especially in those with elevated pretreatment LDH levels, elevated leukocyte count, renal dysfunction, and dehydration. To mitigate the potential risk of TLS, patients will be required to have WBC count <10K prior to initiating venetoclax on C1D8 and will receive TLS prophylaxis prior to venetoclax initiation on C1D8 and prior to venetoclax dose escalation. Patients will be hospitalized on Day -1 (C1D7) of venetoclax through at least 24 hours post target cohort dose. Thus it is projected that if WBC is <10K on C1D7, patients will be hospitalized C1D7 (day -1 venetoclax) through C1D12 (24 hours post venetoclax dose escalation completed).

Venetoclax will be administered at a dose of 50 mg on day 8, 100 mg on day 9, 200 mg on day 10, and 400mg on days 11-28 of the first cycle. All subsequent cycles, Venetoclax will begin on Day 1. For toxicities that could be attributed to either drug, Venetoclax or Quizartinib or both could be held or modified, based on perceived contribution (as per treating physician, in discussion with PI) of respective drug to the toxicity. This schedule may need to be adjusted if we see any signs of TLS. If this occurs it should be discussed with the PI and the new schedule documented in the patients chart.

To mitigate the risk for TLS, subjects must be receiving tumor lysis prophylaxis, including hydration (oral, intravenous) and treatment with a

uric acid reducing agent (allopurinol, rasburicase) at least 24 hours prior to the first dose of venetoclax and during the venetoclax ramp up period of Cycle 1.

TLS chemistry tests (potassium, uric acid, creatinine, calcium and phosphorus) will be obtained prior to dosing and 6-8 hours after each day of a new venetoclax dose. TLS chemistry test results will be reviewed by the investigator in real time and prior to the subject's next dose to ensure appropriate management. If a subject meets criteria for clinically significant laboratory or clinical TLS, no additional venetoclax should be administered until resolution.

Venetoclax interruption for up to 72 hours following transient (< 48 hours) chemical changes and laboratory TLS will be allowed and will not require a dose reduction.

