5.5.7 DRUG DRUG INTERACTION ASSESSMENT

Both quizartinib and venetoclax are CYP3A and Pgp substrates. Both quizartinib and venetoclax are Pgp inhibitors, and the latter also inhibits BCRP. Therefore, the potential for a two way drug drug interaction will be assessed in a substudy of the first 12 subjects enrolled in the Phase 1b. Specifically this substudy will assess the effect of venetoclax on quizartinib PK (i.e. Cmax and AUC0-24h) and the effect of quizartinib on venetoclax PK (i.e. Cmax and AUC0-24h) as summarized in section 5.1.

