Bone marrow samples:

- At screening (within 14 days preceding study initiation) as per section 7.1.8 – This BM will be done after the patient is consented to the study
- Cycle 1 day 8 (prior to the first dose of venetoclax)
- At the time of disease assessment on day 28 (+/- 4 days)
- At response assessment pre-cycle 4 (EOC 3)
- At progression/relapse (if sample available)
- Missed samples or cycles outside the provided time windows for correlative studies and/or for PK analysis will not constitute

protocol deviations. These studies are optional on this protocol.

7.2.10 All treatment prescriptions for quizartinib and venetoclax must be written by the patient's attending physician at MDACC or the PI of the study. We do not intend for the subjects to receive prescriptions for quizartinib or venetoclax at an outside physician's office. During the first cycle all the protocol required laboratory evaluations will be done at MDACC. Subsequently, the patient may have the laboratory work done at a local clinic and the results reported to the research nurse for the study. The laboratory work done at the local clinic will be forwarded to the patient's attending physician at MDACC or PI of the study, who will sign off on the labs to verify that the results have been reviewed.

Outside Physician Participation During Treatment

1. MDACC Physician communications with the outside physician is required prior to the patient returning to the local physician. This will be documented in the patient record.
2. A letter to the local physician outlining the patient's participation in a clinical trial will request local physician agreement to supervise the patient's care.
3. Protocol required evaluations outside MDACC will be documented by telephone, fax or e-mail. The PI/treating physician must review the labs, determine clinical significance and sign and date the report.
4. A copy of the informed consent, protocol abstract, treatment schema and evaluation during treatment will be provided to the local physician.
5. Documentation to be provided by the local physician will include progress notes, reports of protocol required laboratory and diagnostic studies and documentation of any hospitalizations.
6. The home physician will be requested to report to the MDACC physician investigator all life threatening events within 24 hours of documented occurrence.
7. All follow-up visits that correspond with drug dispensation will be performed at MDACC.

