11.1 Phase Ib (Lead-in Phase)

The phase Ib portion is aimed at finding the MTD and RP2D of the two drugs in this combination. We plan to select a RP2D based on efficacy, toxicity, and PD data from the phase 1b dose-escalation. 3 patients at each dose level may not be sufficient to get a good estimate of efficacy and PD changes, and thus 6 patient dose escalation schema is proposed.

Patients will be enrolled in cohorts of 6 patients in the phase Ib portion of the study. The target dose is dose level +1, and the starting dose will be dose level 0. The first 6 patients on study will receive dose level 0.

The MTD is defined as the highest dose level with ≤ 1 out of 6 patients experience a DLT during the first 28 days of treatment. DLT is defined in section 3.4. The planned dosing algorithm is presented in section 3.3 and the dosing schema for the combination treatment is shown in Table 1. The RP2D will be selected at the end of the phase I portion based on reviewing the safety, efficacy, and PD data of quizartinib and venetoclax after discussion between the PI/Co-PI, the sponsor (MDACC IND office), and the supporting companies (Daiichi-Sankyo and Abbvie Inc). The Investigator is responsible for completing the cohort summary template prior to advancing subjects to the phase II part. Once RP2D has been established, any patients still on study at a dose lower than RP2D can be dose escalated up to RP2D in accordance with the dose-escalation guidelines in section 5.2.3.

The PK of quizartinib will be summarized statistically as n, geometric mean, %CV, median, minimum and maximum as Cmax and AUC0-24h of quizartinib and AC886 collected on Cycle 1 Day 7 (quizartinib alone) and Cycle 1 Day 8 (quizartinib + venetoclax) for the first 12 subjects. PK parameters will be dose normalized.

The PK of venetoclax will be summarized statistically as n, geometric mean, %CV, median, minimum and maximum for Cmax and AUC0-24h of venetoclax and M27 collected on Cycle 1 Day 8 (venetoclax + quizartinib) for the first 12 subjects. PK parameters will be dose normalized.

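### Section 11.1 summarises PK profiles on Cycle 1 Days 7 and 8 that Section 5.1 never schedules, and this leaves the interaction substudy without the reference profiles it needs

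*Combined protocol and SAP*

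**What the plan says.** All references are to the combined protocol and SAP.

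- **Section 5.1 (Schedule)** sets one serial collection in the 12 dose-escalation patients: pre-dose, then 2, 4, 6, 8 and 24 "hours post-dose on cycle 1 day 14 to measure venetoclax, quizartinib and AC886 concentrations". Venetoclax is intended to start on Cycle 1 Day 8, so Day 14 is a combination day.
- **Section 11.1 (Phase Ib)** will summarise Cmax and AUC0-24h for quizartinib and its metabolite AC886, with samples "collected on Cycle 1 Day 7 (quizartinib alone) and Cycle 1 Day 8 (quizartinib + venetoclax) for the first 12 subjects", and the same parameters "of venetoclax and M27 collected on Cycle 1 Day 8". The summaries are descriptive (n, geometric mean, %CV, median, range) and dose normalised.
- **Section 5.5.7** promises to assess the effect of venetoclax on quizartinib, and "the effect of quizartinib on venetoclax PK (i.e. Cmax and AUC0-24h) as summarized in section 5.1". It gives no day and no metabolite of its own.
- **Section 5.5.4** sets the first-cycle venetoclax ramp-up: "at a dose of 50 mg on day 8, 100 mg on day 9, 200 mg on day 10, and 400mg on days 11-28".
- **Section 7.2.9** does not treat gaps in these samples as deviations (the sentence begins "Missed samples or cycles outside the provided time windows for correlative studies and/or for PK analysis will not constitute"), and it calls the work optional: "These studies are optional on this protocol".

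**The concern.** The analysis section and the schedule describe different data. A team that follows 5.1 will hold Day 14 samples for which no analysis is written, and will have nothing to enter into the analysis that is written. M27 is named only in 11.1.

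What is at stake is the interaction question. Section 5.5.7 raises it because both drugs are CYP3A and P-gp substrates and both inhibit P-gp. To show within patients that one drug changes the exposure of the other, each drug needs a profile without its partner. The two sections disagree on whether such a profile exists for quizartinib, and neither provides one for venetoclax.

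**Working it through.** **Step 1. Profiles needed against profiles scheduled.**

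| Profile (Cmax, AUC0-24h) | Summarised in 11.1 | Sampled in 5.1 |
|---|---|---|
| Quizartinib, Day 7 | yes | no |
| AC886, Day 7 | yes | no |
| Quizartinib, Day 8 | yes | no |
| AC886, Day 8 | yes | no |
| Venetoclax, Day 8 | yes | no |
| M27, Day 8 | yes | no |
| Quizartinib, Day 14 | no | yes |
| AC886, Day 14 | no | yes |
| Venetoclax, Day 14 | no | yes |

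The overlap is 0 of 6. The number of patients does agree: two cohorts of 6 give 12 in both sections. No other section schedules serial PK; the Day 8 blood draw in 7.2.9 is an optional pharmacodynamic sample taken before the first venetoclax dose.

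**Step 2. Single-agent reference for each direction in 5.5.7.**

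| Direction | If 5.1 governs | If 11.1 governs |
|---|---|---|
| Venetoclax on quizartinib | no quizartinib-alone profile | Day 7 reference; combination day is Day 8 |
| Quizartinib on venetoclax | no venetoclax-alone profile | no venetoclax-alone profile |

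References available: 0 of 2 under 5.1 and 1 of 2 under 11.1. In that one case the venetoclax dose on Day 8 is 50 mg, and 50/400 = one eighth of the full dose. Dose normalisation rescales a drug's exposure by its own dose. It does not turn a first 50 mg venetoclax dose into a test of what 400 mg does to quizartinib.

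**Step 3. How far accumulation alone moves a quizartinib ratio.** Section 2.2 gives a terminal half-life of about 100 h and an AUC accumulation ratio of 5.7. In a linear one-compartment model with daily dosing, the accumulation ratio is R = 1/(1 − r), where r = exp(−24 × ln2 / half-life). R = 5.7 gives r = 1 − 1/5.7 = 0.825, a half-life of about 86 h. The fraction of steady-state AUC on Day n at constant dose is f(n) = 1 − rⁿ.

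| Half-life | f(7) | f(8) | f(14) | Day 8/Day 7 | Day 14/Day 7 |
|---|---|---|---|---|---|
| 86 h | 0.741 | 0.786 | 0.933 | 0.786/0.741 = 1.06 | 0.933/0.741 = 1.26 |
| 100 h | 0.688 | 0.736 | 0.903 | 0.736/0.688 = 1.07 | 0.903/0.688 = 1.31 |

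With no interaction at all, the ratio would be about 1.06-1.07 for Day 8/Day 7, or 1.26-1.31 for Day 14/Day 7. The documents plan neither ratio; these values show what one would have to be read against.

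**The case against.** The best defence is that PK is peripheral here. Section 7.2.9 calls these studies optional, 11.1 plans only descriptive summaries, and 5.5.7 does not promise a within-patient comparison. Section 3.3 says: "The RP2D will be selected from among the doses evaluated after reviewing the efficacy, safety, pharmacodynamics data". PK is not in that list. The Phase Ib objective in 1.2 is to characterise the PK of the combination, which the Day 14 set does.

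Most of that stands, and it limits the severity. It does not remove the contradiction. Excusing a missed or out-of-window sample is not the same as supplying a day that was never scheduled, and it does not say which section governs. If 11.1 is taken as the true schedule, the Day 14 set has no planned analysis and 5.5.7 points to the wrong section, so an edit is needed either way.

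Three stronger readings are tempting, and the documents do not support them.

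- A reader might infer a three-way conflict. Section 5.5.7 states no schedule of its own; it inherits the one in 5.1.
- A reader might infer that dose selection or the efficacy decision is compromised. Neither uses PK.
- A reader might put one bias figure on patients stepped up to 60 mg. Section 5.1 makes the increase depend on a Day 12 post-dose ECG, which 7.2.8 allows within ±2 days. The number of 60 mg doses by Day 14 is therefore not fixed. Under the same model, assuming dose proportionality, the Day 14 AUC would be (f(14) + f(m))/2 of the 60 mg steady state after m such doses: about 65-69% for three doses, 59-63% for two, and less after a late ECG.

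**Conclusion.** The point holds as a contradiction between 5.1 and 11.1. Under 5.1 as written, 0 of the 6 profiles in 11.1 can be computed and M27 is not measured. It follows that 5.5.7 lacks a quizartinib-alone reference if 5.1 governs and lacks a venetoclax-alone reference in any case.

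The counts rest on the text alone, with venetoclax starting on Day 8 as intended; the actual start also requires a WBC count below 10K. The accumulation figures are approximate: they assume linear kinetics and constant dose, whereas the steady-state means in Section 2.2 rise 8276/3370 = 2.46-fold for a doubled dose.

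The effect is confined to the Phase Ib secondary PK objective and the interaction substudy. It should be corrected, but it does not threaten the trial's main conclusions.

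**What to change.** Reconcile 5.1 and 11.1 on sampling days and analytes, and make 5.5.7 consistent with the result. There are two workable routes.

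1. **No extra sampling.** Let 11.1 summarise the Day 14 combination profile that 5.1 collects. Drop M27, or add it to the 5.1 assay. State in 5.5.7 that both directions are descriptive comparisons with external single-agent values. This costs wording only, plus an assay if M27 is kept.
2. **Keep the Day 7 quizartinib-alone profile.** Add it to 5.1, completed before the first venetoclax dose, and settle M27 as above. Report any quizartinib ratio beside the accumulation expected without interaction, and still label the effect of quizartinib on venetoclax as an external comparison. This costs one extra serial blood set in up to 12 patients.

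If sampling is already complete, state which days were sampled and label the results accordingly.

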The major circulating moieties are unchanged quizartinib and AC886 (> 10% of the total radioactivity exposure in plasma). AC886 has similar potency and selectivity to quizartinib and has been measured in all clinical studies with quizartinib PK assessments. The median Tmax for AC886 ranged from approximately 5 to 8 hours across studies in healthy volunteers. The ratio of AC886 to quizartinib (AUClinf) was approximately 0.5 at steady state.

Elimination: The principal route of excretion was hepatobiliary, estimated as > 90%. Renal excretion was a minor route of elimination (< 2%). The terminal elimination half-lives for quizartinib and AC886 are approximately 100 hours. For quizartinib 60 mg QD, the observed geometric mean accumulation ratios (AUC0-24h) for quizartinib and AC886 were 5.7 and 8.2, respectively.

Safety

A cardiovascular safety pharmacology study in cynomolgus monkeys demonstrates that single oral doses of quizartinib result in prolonged QTc interval at ≥ 10 mg/kg doses and biologically significant increased systolic blood pressure at ≥ 100 mg/kg doses. It should be noted that increases in blood pressure were not observed in the Phase 1 dose-escalation study, Protocol AC220-CP0001; henceforth called Study CP0001(33). No QTc interval prolongation was evident in monkeys dosed with 3 mg/kg quizartinib. It is suggested that quizartinib and AC886 induced blockade of human ether-à-go-go-related gene (hERG) current and I_{Ks} , and therefore caused QT prolongation by a decrease in the net repolarization currents. The effect on I_{Ks} was more dominant than that on hERG. There were no apparent electrocardiogram (ECG) abnormalities in the dog (28- and 90-day) or monkey (28- and 90-day) general toxicology studies. In addition, there were no apparent toxicologically relevant quizartinib-related heart microscopic changes in the rat, dog, or monkey general toxicology studies.

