- 7.2.8 EKG will be performed on day 1, day 5, day 8, and day 12 of the first cycle (all ± 2 days) Day 1 and day 8 ECG are collected pre-dose; day 5 are collected pre-dose and 4 hrs (+/- 2 hrs) post-dose; day 12 are collected 4 hrs (+/- 2 hrs) post-dose. Then ECG to be done on day 1 of each cycle for cycles 2, 3, 4 and 5 before initiation of quizartinib and 4 hr (+/- 2 hrs) post dose, then pre-dose every 2 subsequent cycles. EKG may be omitted if patient has not received study drug (quizartinib) in the 48 hrs preceding the time when EKG is done. EKG at screening and for the first 3 cycles will be done in triplicate. Subjects **should rest in the supine position or semi-recumbent, with the same position used for an individual subject for the duration of the study, for at least 5 minutes before each 12-lead ECG recording is started. The ECGs should be reviewed, signed,**

and dated by a qualified physician (or qualified physician's assistant or nurse practitioner) and any clinically important finding recorded on the appropriate eCRF. The results will include heart rate, PR interval, QRS interval, QT interval, and QTcF interval. QTcF is calculated using the formula, $(QT)/3\sqrt{RR}$. All screening and on study ECGs should be obtained in triplicate (10 seconds for each ECG over the 5-minute period).

- A. On patients who increase the dose of Quizartinib or start therapy with a drug that is a moderate CYP3A4 inhibitor, an EKG will be required 24 hrs (± 6 hrs), 7 days (± 2 days) and 14 days (± 2 days) after the dose increase or after the start of the moderate CYP3A4 inhibitor.
- B. Patients who had their dose reduced because of QTc prolongation and have their dose re-escalated as described in section 5.2.3 will have an EKG repeated 24 hrs (± 6 hrs) and 7 days (± 2 days) after re-escalation.
- C. The QTc interval will be calculated by Fridericia's correction factor (QTcF). The 12-lead EKG evaluation will consist of 3 separate EKGs obtained at least 5 minutes apart.

7.2.9 Peripheral blood (up to 40 cc each time) and bone marrow (up to 15 cc each time) for pharmacodynamic studies (Optional) as defined in section 6.0 on

Peripheral blood:

- Prior to first dose of quizartinib at baseline (Cycle 1 Day 1).
- Cycle 1 Day 8: prior to the first dose of venetoclax
- Cycle 1 Day 15: prior to the dose of quizartinib and venetoclax (steady state)
- Cycle 1 Day 28 (+/- 4 days): prior to the dose of quizartinib and venetoclax
- At progression/relapse (if sample available)

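### Dose-normalizing quizartinib PK on Day 14 would read level +1 about 28–34% below level 0 with no interaction; the PK days in 11.1 and 5.1 conflict, and the Day 15 steady-state label does not fit level +1

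*Combined protocol and SAP*

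**What the plan says.** - **Aim.** Section 5.5.7: "this substudy will assess the effect of venetoclax on quizartinib PK (i.e. Cmax and AUC0-24h", together with the effect of quizartinib on venetoclax. It refers to Section 5.1 for the details.
- **Sampling in the treatment plan.** Section 5.1 has one PK day, with samples from pre-dose to 24 "hours post-dose on cycle 1 day 14 to measure venetoclax, quizartinib and AC886 concentrations in patients enrolled in the dose-escalation period (n=12").
- **Sampling in the analysis.** Section 11.1 instead summarises parameters "collected on Cycle 1 Day 7 (quizartinib alone) and Cycle 1 Day 8 (quizartinib + venetoclax) for the first 12 subjects". The summary is n, geometric mean, %CV, median, minimum and maximum, and the paragraph closes with "quizartinib + venetoclax) for the first 12 subjects. PK parameters will be dose normalized". It does not say which dose is the divisor and makes no allowance for accumulation.
- **Kinetics.** Section 2.2: "The terminal elimination half-lives for quizartinib and AC886 are approximately 100 hours". At 60 mg once daily, "the observed geometric mean accumulation ratios (AUC0-24h) for quizartinib and AC886 were 5.7 and 8.2, respectively". The same section gives steady-state geometric mean AUC0-24h of 3370 at 30 mg and 8276 ng·h/mL at 60 mg.
- **Dosing history.** Section 5.1 keeps level 0 at 30 mg from Day 1. Level +1 also starts at 30 mg and "can increase to quizartinib 60mg per day on C1D12 only if QTcF on triplicate ECG is <450 msec", read on a post-dose ECG.
- **PD sampling.** Section 7.2.9 lists an optional blood sample: "Cycle 1 Day 15: prior to the dose of quizartinib and venetoclax (steady state"). It does not separate the dose levels.

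**The concern.** Dividing an AUC by the current dose assumes that exposure has already moved in proportion to that dose. With a half-life near 100 hours, five half-lives are 500/24 ≈ 21 days, so a Day 14 AUC at level +1 still mostly reflects the earlier 30 mg dosing. Day 14 is the only PK day in the treatment plan and gives no quizartinib-alone profile. Only comparison between levels, or with historical values, is then possible, and that is where the normalized figure misleads. It errs towards hiding a rise in quizartinib exposure, which matters because both drugs are CYP3A and P-gp substrates (Section 5.5.7) and quizartinib's QTcF effect is dose dependent (Section 2.2).

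The same kinetics bear on the Day 15 PD sample. Sections 3.3 and 11.1 use PD data in choosing the RP2D, and anyone who takes the label at face value would assume a two-fold exposure contrast between levels that is not yet present.

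**Working it through.** **Inputs.** Half-life t ≈ 100 h; accumulation ratios 5.7 and 8.2; steady-state AUCs 3370 and 8276 (all Section 2.2). Dosing from Section 5.1. Assumptions: linear one-compartment superposition, dosing every 24 h, no missed doses, no true interaction.

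**Formulas.** Accumulation ratio R = 1/(1 − 2^(−24/t)). AUC0-24h on day n of constant dosing, as a share of steady state: f(n) = 1 − 2^(−24n/t). The Day 15 pre-dose level has the same share as f(14). At level +1 on Day 14, with k doses of 60 mg given, the share of 60 mg steady state is [f(14) + f(k)]/2.

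**The plan's own figure.** R at 100 h is 6.53, against the stated 5.7 (14% above it) and 8.2 (20% below it). Inverting R, the stated ratios imply effective half-lives of 86 h and 128 h. These bracket about 100 h, so the stated figures are not treated as wrong; 86–128 h is the sensitivity range.

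**Shares at 100 h.** f(2) = 0.283, f(3) = 0.393, f(7) = 0.688, f(8) = 0.736, f(14) = 0.903.

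**Days 7 and 8 (Section 11.1).** Day 8/Day 7 = 0.736/0.688 = 1.07 (range 1.06–1.08). This is the same at both levels, because both days precede the step and every patient at level 0 or +1 has had only 30 mg. Dividing level +1 values by the assigned 60 mg instead would multiply them by 30/60 = 0.5.

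**Day 14 (Section 5.1).** Three 60 mg doses if the step is taken on Day 12; two if the post-dose ECG delays it to Day 13.

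| Quantity | Three 60 mg doses | Two 60 mg doses |
|---|---|---|
| Level +1 share of 60 mg steady state | (0.903 + 0.393)/2 = 0.648 (0.58–0.69) | (0.903 + 0.283)/2 = 0.593 (0.53–0.63) |
| Per-mg AUC, level +1 / level 0 | 0.648/0.903 = 0.72 (0.69–0.74) | 0.593/0.903 = 0.66 (0.64–0.67) |
| Raw AUC, level +1 / level 0 | 1.44 | 1.31 |

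Level 0 itself is at 90% of steady state (84–93%).

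**Allowing for non-proportional AUCs.** The stated AUCs give 3370/30 = 112 and 8276/60 = 138 per mg, a ratio of 1.23. Level 0 on Day 14 is 3370 × 0.903 ≈ 3042. Adding (8276 − 3370) × f(k) gives 4969 (three doses) or 4430 (two) at level +1. The per-mg ratios become (4969/60)/(3042/30) = 0.82 and (4430/60)/(3042/30) = 0.73, so the deficit is 18–27%. It is smaller and in the same direction. The raw contrast becomes 1.63 or 1.46.

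**What this could hide.** Against a 60 mg steady-state reference, a true rise of 1/0.648 = 1.54-fold (three doses) or 1/0.593 = 1.69-fold (two) at level +1 would look like no change.

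**Day 7 paired with Day 14.** At level 0: 0.903/0.688 = 1.31 (1.26–1.40). At level +1, per mg: 0.648/0.688 = 0.94 or 0.593/0.688 = 0.86. No section plans this pair.

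**Day 28 PD sample.** Pre-dose on Day 28, level +1 is at (f(27) + f(16))/2 = (0.989 + 0.930)/2 = 0.96 with the step on Day 12, or 0.95 with the step on Day 13. The contrast with level 0 is 1.94 or 1.93.

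**The case against.** The strongest reply is that Section 11.1, where the normalization rule stands, plans Days 7 and 8. On those days normalizing by the dose actually given distorts nothing and accumulation adds 7% alike at both levels. The summaries are descriptive, with no interaction test or threshold; between-patient CVs for AUC are 72.5% and 95.7%; PK is not among the listed RP2D inputs; the step is conditional; the Day 15 sample is optional; and Section 11.3 plans PD changes from baseline to response and to progression, not a Day 15 comparison between levels.

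Most of that stands and limits the point. It does not remove it. Section 5.1 schedules only Day 14, and the interaction section refers there. The divisor is left unnamed even for Days 7 and 8. A systematic shift of this kind does not average out across patients, however wide the CV.

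A reader might infer more than the documents support:
- **That accumulation will be mistaken for an interaction at level 0.** The 31% rise needs a Day 7/Day 14 pair that no section plans. If Day 14 were compared with historical steady state instead, level 0 would read about 10% low.
- **That a false rise at level 0 and a false fall at level +1 cancel when pooled.** The 28–34% deficit is a between-level contrast. The within-patient Day 14/Day 7 change at level +1 would be a fall of 6–14%. Section 11.1 does not say that levels are pooled.
- **That the problem is the same whichever PK day is used.** The Day 12 step cannot touch Days 7 and 8.

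**Conclusion.** The point holds in a limited form. The sampling days in 11.1 and 5.1 contradict each other, and the normalization rule is unsafe on the one PK day the treatment plan schedules. On Day 14, level +1 is at about 65% (58–69%) of 60 mg steady state after three 60 mg doses, or 59% (53–63%) after two. Its dose-normalized AUC is then 28–34% below level 0 at a 100 h half-life (18–27% with the stated AUCs) without any interaction. On Days 7 and 8 the only risks are a 7% drift and a halving if the assigned dose is the divisor.

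The Day 15 label is close for quizartinib at level 0 (about 90%) but wrong at level +1 (59–65%). For AC886 the 128 h effective half-life gives about 84% at level 0; this is rougher, because AC886 is formed from the parent drug.

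These figures rest on linear superposition, full adherence and the step being taken on Day 12 or 13. A level +1 patient who stays at 30 mg has level 0 kinetics. Any effect on dose selection is indirect.

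**What to change.** In Section 11.1:
1. Reconcile the PK sampling days with Section 5.1. This comes first, because a per-patient alone-versus-combination ratio cannot be computed from Day 14 alone.
2. Name the administered dose as the divisor. Do not dose-normalize quizartinib or AC886 parameters for a patient whose quizartinib dose changed within the previous five half-lives; report these by dose level and actual dosing history.
3. If an alone day and a combination day are both sampled, express each patient's ratio relative to the accumulation expected from that patient's recorded doses, shown over half-lives of about 86–128 h.

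In Section 7.2.9, qualify the Day 15 steady-state label by dose level. If PD is compared between levels for the RP2D, prefer the existing Day 28 sample.

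The normalization and labelling changes need only wording and a short calculation, with no extra patients. Whether sampling changes depends on how the PK days are reconciled. The correction depends on the assumed half-life, hence the range, and on complete quizartinib dosing records: Section 5.1 describes pill counts for venetoclax but only self-administration for quizartinib, so the source of those records should be stated.
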